#### **Unit-level data**

**C. difficile Infection:** The development of *C. difficile* infection will be determined by standard clinical care which is the presence of clinical symptoms and positive laboratory results. In both the intervention and control groups, hospital-onset (HO)-CDI will be collected monthly as a unit aggregate rate. In this case, hospital refers to the study unit. Research personnel will collect these data from site personnel (i.e., infection control) at participating sites which are collected as usual standard of care. The CDC definition of HO-CDI, used by the VA, is defined as: 1) LabID Event specimen collected >3 days after admission to the facility (i.e., on or after day 4) and 2) CDI-positive laboratory assay: A positive laboratory test result for *C. difficile* toxin A and/or B, (includes molecular assays [PCR] and/or toxin assays) tested on an unformed stool specimen (must conform to the container) OR A toxin-producing *C. difficile* organism detected by culture or other laboratory means performed on an unformed stool sample (must conform to the container). The data will be uploaded to a shared database on the VA server, unless otherwise specified in a valid DUA.

**Other Healthcare-Associated Infections:** The incidence of other HAIs including: 1) catheter-associated bloodstream infection (CLABSI), 2) catheter-associated urinary tract infection (CAUTI), and 3) MRSA HAIs will be measured. HAI data will be collected monthly for both the intervention and control groups using standard CDC/VA definitions. Research staff will collect monthly aggregate data from site personnel (i.e., infection control) at participating sites which are collected as standard of care reporting to VA IPEC (inpatient evaluation center) and/or from VA administrative records. The rate will be calculated by the number of CAUTI or CLABSI per number of device days (i.e., Foley catheters or central lines)  $\div$  1,000 and the number of MRSA infections per number of patient days  $\times$  1000. The data will be uploaded to a shared database on the VA server, unless otherwise specified in a valid DUA.

**Mortality:** In both the intervention and control groups, research staff will collect monthly aggregate 30-day mortality ratio data from site personnel (i.e., nurse manager) at participating sites which are collected as standard of care reporting to VA IPEC and/or from VA administrative records. The data will be uploaded to a shared database on the VA server, unless otherwise specified in a valid DUA.

**Length of Stay:** In both the intervention and control groups, research staff will collect monthly aggregate length of stay (i.e., the number of days spent in the participating unit based on unit admission and unit discharge) data from site personnel (i.e., nurse manager) at participating sites which are collected as standard of care reporting to VA IPEC and/or from VA administrative records. The data will be uploaded to a shared database on the VA server, unless otherwise specified in a valid DUA.

#### **Intervention Fidelity Data:**

**Hand Hygiene Compliance:** In both the intervention and control groups, hand hygiene compliance will be measured on a random sample of healthcare workers caring for patients. Research staff will perform monthly observations that will be recorded on a standard observation tool; participating site research staff will be trained by study coordinating site research staff. WHO manual for observers recommends observing a minimum of 200 hand

hygiene opportunities during each measurement period in each unit. We estimate the number of hand hygiene opportunities as 10 opportunities per patient per hour. The average unit will have 20 patients, therefore each month research personnel will observe hand hygiene opportunities for one hour to generate the minimum observation of 200 hand hygiene opportunities per unit per month. The data will be uploaded to a shared database on the VA server, unless otherwise specified in a valid DUA.

**Contact Precaution Compliance:** In both the intervention and control groups, barrier precaution compliance (i.e., healthcare worker glove plus gown use during care of patients in CP isolation) will be measured on a random sample healthcare worker contacts during care of patients in CP isolation. Research staff will perform monthly observations that will be recorded on a standard observation tool; participating site research staff will be trained by study coordinating site research staff. We estimate the average number of patient contacts by healthcare workers using barrier precautions to be 60 contacts per day. The average unit will have 2-6 patients (10-30%) in CP isolation; each month research personnel will observe for one hour to generate 10% sample of 12 healthcare worker contacts using minimum estimate of patients in isolation. The data will be uploaded to a shared database on the VA server, unless otherwise specified in a valid DUA.

**Universal Gloving Compliance:** In the intervention group, universal gloving compliance will be measured on a random sample of healthcare workers caring for patients. Research staff will perform monthly observations that will be recorded on a standard observation tool; participating site research staff will be trained by study coordinating site research staff. We will use hand hygiene opportunity estimates as surrogate for patient contact opportunities requiring gloving. The average unit will have 20 patients, therefore each month research personnel will observe gloving opportunities for one hour to generate the minimum observation of 200 patient contact opportunities per unit per month in the intervention unit only. The data will be uploaded to a shared database on the VA server, unless otherwise specified in a valid DUA.

**Isolation Days of Care:** Contact precautions can be used for reasons other than CDI such as antibiotic resistant organisms (e.g., MRSA). If a large proportion of barrier precautions are being used in the control group for these types of patients, it could confound the study endpoints. To account for this, we will collect and estimate isolation days of care. In both the intervention and control groups, research staff will collect monthly aggregate data on isolation patients from site personnel (i.e., infection control) at participating sites which are collected as standard of care reporting. We will estimate the isolation days of care by multiplying the number of patients on CP isolation by the average length of stay for the participating unit. The data will be uploaded to a shared database on the VA server, unless otherwise specified in a valid DUA.

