### **5.8 Data Analysis**

#### **5.7.1 Sample Size Determination**

Initial power calculation determined that 10 patient units are necessary to detect a 36% relative reduction (6.2%) in acquisition of *C. difficile* in the intervention vs. no reduction in the control group based on a presumed rate of 9.7 acquisitions per 1,000 patient days; recent literature report an average *C difficile* acquisition rate of 9.7 per 1,000 patient-days and expected reduction of *C. difficile* acquisition of 36%. Each arm of the study will require 9,879 patient days of care. On average, it is estimated that each patient unit will have a 25-bed capacity with an estimated 100 admissions per month and 5-day length of stay. We will plan to enroll 10 units, 5 for each arm. These power calculations will be revised based on actual baseline-period data. The statistical power calculation was conducted using G\*Power. We have incorporated an intracluster coefficient of 0.40 for this study.

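### The one-hour monthly observation rule does not secure the stated minimum of 200 hand hygiene or gloving opportunities per unit

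*Combined protocol and SAP*

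**What the plan says.** All of this is in the combined protocol and SAP.

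- **Section 5.6, Hand Hygiene Compliance.** The rate is "We estimate the number of hand hygiene opportunities as 10 opportunities per patient per hour". The section continues: "The average unit will have 20 patients, therefore each month research personnel will observe hand hygiene opportunities for one hour", and the purpose is "to generate the minimum observation of 200 hand hygiene opportunities per unit per month". The minimum of 200 per unit and measurement period is taken from a cited observer manual. Compliance is to be measured on a random sample of workers.
- **Section 5.6, Universal Gloving Compliance.** The hand hygiene estimate serves "as surrogate for patient contact opportunities requiring gloving". With 20 patients and one hour, the plan expects "to generate the minimum observation of 200 patient contact opportunities per unit per month in the intervention unit only". Again the measurement is on a random sample of workers.
- **Section 5.6, Contact Precaution Compliance.** Contacts using barrier precautions are estimated "to be 60 contacts per day". With 2–6 patients in isolation, one hour is expected to give a 10% sample of 12 contacts at the lower number of patients.
- **Section 5.7.1, Sample Size Determination.** The average unit has "25-bed capacity with an estimated 100 admissions per month and 5-day length of stay".

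**The concern.** Two inputs to the figure of 200 sit uneasily with other parts of the plan. The census of 20 is not what the admissions and length of stay in section 5.7.1 produce. The gloving rate of 10 per patient-hour is borrowed from hand hygiene, while the only contact rate the plan gives is far lower. In addition, 200 is what the whole unit would generate in an hour, whereas the method describes a sample.

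Gloving compliance is the direct evidence that the intervention was delivered. If the trial shows no effect, it helps to separate an ineffective intervention from one that was not carried out. Section 5.7.2 compares compliance between arms and follows it by month, and section 5.7 (Safety Monitoring) uses hand hygiene compliance as a signal that can prompt a response at a site. Monthly figures thinner than planned would weaken these uses.

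**Working it through.** **1. The plan's own figure.** Inputs from Hand Hygiene Compliance: 10 opportunities per patient-hour, 20 patients, 1 hour.

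10 × 20 × 1 = 200. The figure reproduces exactly.

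**2. What 200 requires of the observer.** 3,600 s / 200 = one opportunity every 18 seconds, across all 20 patients. Any opportunity not seen leaves the count below 200, even at a census of 20. The plan does not fix the number of observers. Sections 4.2 and 8.0 assign one research assistant, at 20% effort, to each site, which has two units.

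**3. Census from section 5.7.1.** 100 admissions × 5 days = 500 patient-days per month.

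| Days in month | Mean census (500 / days) | Opportunities per hour (× 10) | Hours for 200 |
|---|---|---|---|
| 28 | 17.9 | 179 | 1.12 |
| 30 | 16.7 | 167 | 1.20 |
| 30.4 | 16.4 | 164 | 1.22 |
| 31 | 16.1 | 161 | 1.24 |

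For an average month the shortfall is (200 − 167)/200 ≈ 17% to (200 − 164)/200 = 18%. It applies to hand hygiene and, through the surrogate, to gloving.

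**4. Contact rate for gloving.** The surrogate implies 10 × 24 = 240 opportunities per patient-day if it holds all day. The Contact Precaution paragraph gives 60 contacts per day. That this is per patient is an inference: the stated 12 equals 10% × 2 patients × 60.

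The same paragraph treats one hour as 10% of a day's contacts, so 6 per patient-hour. Applied to gloving:

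- census 20: 20 × 60 × 10% = 120 per hour
- census 16.7: 16.7 × 60 × 10% ≈ 100 per hour

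The plan does not say how contacts spread over the day. Other assumptions (census × 60 / hours) give:

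| Contacts assumed to fall within | Per hour, census 20 | Per hour, census 16.7 |
|---|---|---|
| 24 h | 50 | 42 (41 at 16.4) |
| 12 h | 100 | 83 |
| 8 h | 150 | 125 |
| 6 h | 200 | 167 |

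At a census of 20, this rate reaches 200 only if all 60 contacts fall within 6 hours.

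**5. Precision of one unit-month.** Assume 80% compliance and independent observations. The half-width is 1.96 × √(0.8 × 0.2 / n).

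| n | 95% half-width, points |
|---|---|
| 200 | 5.5 |
| 165 | 6.1 |
| 120 | 7.2 |
| 100 | 7.8 |
| 50 | 11.1 |
| 41 | 12.2 |

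**The case against.** The strongest reply is that nothing has been miscalculated. The rate, the census and the hour are stated together and multiply to 200, and the gloving rate is openly called a surrogate. That stands: a reader might infer an arithmetic error, and there is none.

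Three further limits also stand.

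- **The census.** A reader might take 164 as a ceiling. It is a mean built from rounded planning values. Twenty patients is 80% of 25 beds, and a full unit would give 25 × 10 = 250.
- **The contact rate.** A reader might conclude that gloving yields 41–50 observations, not 200. That needs an even 24-hour spread, which the plan does not state and which its own figure of 12 contacts in one hour from two patients contradicts. The 60 per day also describes contacts using barrier precautions, and may not apply to patients outside isolation.
- **The consequence.** The half-widths are for one unit in one month. Even 50 per unit-month over 5 intervention units and 24 months is 50 × 5 × 24 = 6,000 gloving observations. Section 5.7 adds routine infection control data on hand hygiene and protective equipment, and the cost analysis in section 5.6 collects monthly glove supply by unit.

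These points narrow the concern without removing it. The two census figures remain unreconciled, as do the two rates, and 200 still depends on complete capture by a method described as sampling.

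**Conclusion.** The concern holds as an unsecured minimum. One hour gives 200 only with 20 patients present, the surrogate rate holding, and every opportunity seen.

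- On the throughput in section 5.7.1, the expected count is about 164–167, or 17–18% short.
- For gloving, the plan's own contact rate and hourly conversion give about 100–120. The range is 41 to 150 for assumed spreads from 24 down to 8 hours. This rests on reading 60 per day as per patient and on applying it outside isolation.

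The effect is on monthly unit-level fidelity estimates: half-widths of roughly 6 to 12 points in place of 5.5, under the assumptions of 80% compliance and independence. Comparisons pooled by arm are affected less. The documents give no ground for extending the concern to the primary outcome, which comes from admission and discharge specimens. Severity is low: worth correcting, not a threat to the trial.

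**What to change.** In Hand Hygiene Compliance and Universal Gloving Compliance (section 5.6), replace the fixed hour with observation until 200 opportunities are recorded in the unit that month, over as many short sessions as needed. This removes the dependence on every rate and census assumption above.

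If the hour is kept, say that 200 is not guaranteed, and give the expected yield as a range with its assumptions: census, contacts per patient-day, their spread over the day, and the share an observer can see. A single figure of 40–50 should not be written in, because it would present the 24-hour spread as fact.

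In either case, use one census figure in section 5.6 and section 5.7.1.

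Cost: observing to a count takes more time from the existing research assistants. Restating the yield is a wording change, at the price of a less favourable stated number.

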**30-Day Mortality:** Using patient level data, we will conduct a 30-day survival analysis to determine the hazard of mortality for control and intervention units using a cox proportional hazards model with Kaplan Meier curves. Within each unit, a risk analysis will be conducted to

determine the predictors of 30-day mortality. Additionally, we will examine survival percentages at specific periods of the intervention period (i.e. 3, 6, 9 and 12 months; or every 3 months of the intervention period) using life tables and log-rank tests to determine at which points mortality was highest for each unit.

*Other clinical outcomes:* Rates of toxic megacolon and colectomy will be compared between intervention and control units using chi-squared test or Fisher's exact test, with post-hoc pairwise comparisons. All incidence and risk analysis will be conducted using Poisson regression models with covariate adjustment. For specific time periods (during 3, 6, 9 and 12 months), we will use incidence split model to determine the point of highest infection within each unit, with appropriate covariate adjustment. We will use the Royston's trend test to conduct a time-trend analysis on the monthly outcomes.

*Intervention Fidelity:* We will calculate the compliance rates for both the intervention and control units and compare them using a chi-squared test. We will conduct a univariate logistical regression model to determine the odds of compliance with respect to additional unit characteristics such as number of beds and location. Monthly compliance will be modeled using a time series graphing technique with trend analysis estimates.

*Isolation Days of Care:* Monthly aggregate data of isolation patients will be collected from infection control at participating sites which are collected as standard of care and we will estimate the days of care by multiplying this number by the average length of stay for the participating unit. We will make comparisons between the intervention and control groups using the analysis of variance (ANOVA).

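### Isolation days of care are computed as isolated patients times average unit stay, with no denominator, so they cannot reliably show what share of control care is already under barrier precautions

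*Combined protocol and SAP*

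**What the plan says.** Section 5.6 (Intervention Fidelity Data, Isolation Days of Care) gives the reason for the measure. Contact precautions are also used for organisms other than *C. difficile*, and "If a large proportion of barrier precautions are being used in the control group for these types of patients, it could confound the study endpoints".

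For the data, "research staff will collect monthly aggregate data on isolation patients from site personnel". Whether that means new isolations, distinct patients present, or a census is not said. Isolation days are then estimated by "multiplying the number of patients on CP isolation by the average length of stay for the participating unit". Section 5.7.2 repeats the rule ("multiplying this number by the average length of stay for the participating unit") and compares the two groups by ANOVA. No denominator is given in either place.

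Length of stay is a monthly aggregate for the whole unit, defined in section 5.6 as "the number of days spent in the participating unit based on unit admission and unit discharge". It is also a secondary outcome under section 3.0. Isolation start and stop dates and daily isolation counts are not among the data listed for collection.

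For scale, the Contact Precaution Compliance paragraph of section 5.6 says: "The average unit will have 2-6 patients (10-30%) in CP isolation". Section 5.7.1 assumes 100 admissions a month, a 5-day stay and 25 beds per unit.

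**The concern.** Under section 5.2.2, control patients with known CDI or another resistant organism are to be cared for with gloves and gowns. The share of control patient-days under such precautions therefore limits how much additional gloving the intervention can deliver. A null result would read differently with 10% of control care already under precautions than with 30%.

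This is the one measure the plan assigns to describing that background. Universal gloving is observed in intervention units only. Contact-precaution compliance and gloves issued are recorded in both arms, but neither is assigned to this check and neither measures isolation days. If the measure can be wrong in either direction, and is a total where a proportion is needed, it cannot do the job section 5.6 gives it.

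**Working it through.** **Figures in the plan.** The documents state no isolation-days figure, so there is none to reproduce. The neighbouring figures do reproduce: 2/20 = 10% and 6/20 = 30% in isolation; 10% × 2 patients × 60 contacts = 12 observed contacts.

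**True value.** Isolation days in a month = daily isolated census × days in the month. For a census of 2 to 6 over 30 days this is 60 to 180. Take 4 isolated at a time: 4 × 30 = 120.

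**What the formula returns.** Unit stay is 5 days (section 5.7.1). Let L be the stay of isolated patients, isolated throughout. L = 10 and L = 15 are assumptions; the documents give no stay for isolated patients. New isolations per month = 120/L. Distinct patients present = 4 + 120/L, because a patient whose isolation spans two months is counted in both.

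| Meaning of the monthly count | L (days) | Count | Count × 5 | True days |
|---|---|---|---|---|
| New isolations | 5 | 24 | 120 | 120 |
| New isolations | 10 | 12 | 60 | 120 |
| New isolations | 15 | 8 | 40 | 120 |
| Distinct patients present | 5 | 28 | 140 | 120 |
| Distinct patients present | 10 | 16 | 80 | 120 |
| Distinct patients present | 15 | 12 | 60 | 120 |
| Census | any | 4 | 20 | 120 |

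Only the first row is right.

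**Isolation for part of the stay.** Fix the count at 20 new isolations a month. The formula gives 20 × 5 = 100 days, or 20% of 100 × 5 = 500 patient-days. True days = 20 × (stay of isolated patients − days before isolation starts). Both terms are assumed:

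- 5-day stay, isolation starting 1 to 3 days in: 20 × 4 = 80 down to 20 × 2 = 40 days.
- 7.5- to 10-day stay, isolated throughout: 20 × 7.5 = 150 up to 20 × 10 = 200 days.

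Across that range the true share runs from 40/500 = 8% to 200/500 = 40%, while the formula stays at 20%.

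**No denominator.** With 20% of patients isolated, a unit holding 20 patients has 4 × 30 = 120 true isolation days and one holding 25 has 5 × 30 = 150, at the same share. The total also moves with unit stay: 20 isolated patients give 20 × 5 = 100 at a 5-day mean and 20 × 6 = 120 at a 6-day mean. Divided by patient-days (admissions × mean stay), the stay cancels: 100/500 = 120/600 = 20%.

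**The case against.** Four objections carry weight.

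- **The favourable reading is natural.** If the monthly figure is new isolations, patients times stay is the ordinary steady-state estimator and can be exactly right, as the first row of the table shows. Likewise 10–30% of 100 admissions × 5 days gives 50–150 days, which is 10–30% of 500 patient-days and agrees with the plan's expected share. This stands. A reader might infer a six-fold understatement (10–30 days against 60–180), but that needs the count to be a census, which the text does not say.
- **The other sizes are assumed.** Counting 5 days for a patient isolated for only 2 is a 2.5-fold excess for one hypothetical patient, not for a unit-month. A 20% arm difference from stays of 5 and 6 days is false only if isolated days stay fixed while unit stay changes; isolated patients' stays might lengthen too, and the difference would then be real.
- **The measure is supportive and openly called an estimate.** Its only stated use is the ANOVA. The acquisition analyses do not name it as a covariate, so the primary result does not depend on it. A proportional error common to both arms would also preserve their ratio, although it would still misstate the absolute control-arm level that section 5.6 worries about.
- **Dates for every patient would be a new data stream.** Unit data are existing aggregates, patient-level records are planned for consenting patients, and each site has a research assistant at 20% effort (section 8.0).

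These points limit the size of the problem and the remedy. They do not supply the missing definition of the count, the stay of isolated patients, or a denominator.

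**Conclusion.** The concern holds as a weakness in a supportive measure. The formula is correct only under three conditions that the plan does not secure, and the documents fix neither the direction nor the size of the error. The figures above are conditional illustrations, not estimates of bias. The missing denominator needs no assumption: a raw total cannot answer a question about a proportion.

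A reader might go further and infer that the primary comparison is biased, or that the trial would call its arms well separated when they are not. The documents support neither. Even at the assumed extreme of 40% of patient-days in isolation, 60% lie outside precautions, and contact-precaution compliance is itself measured rather than known to be complete. What is weakened is the reading of the contrast between arms, chiefly if the trial finds no difference. The change is worth making but is not critical.

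**What to change.** Amend sections 5.6 and 5.7.2 as follows.

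1. Report isolation as a share of unit patient-days, by unit and within each site pair, beside the acquisition result. Patient-days are already the planned denominator for MRSA infections.
2. For the numerator, use actual patient-days in contact precautions where infection control or administrative records already hold them.
3. Elsewhere, use the proportion of the unit census in contact precautions, recorded at each monthly observation visit and averaged over the study period.
4. If the product is kept anywhere, define the count as new isolation episodes in the month, divide by patient-days, and state that whole-unit stay stands in for days isolated.

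The cost is protocol and SAP wording and a slightly larger monthly data request; the census count needs no extra visit. The fallback is noisy for a single month (4 of 20 has a 95% interval of roughly 6% to 44%), so only averages over many months should be interpreted. Some sites may be able to supply only the census share, and reports should say which source each unit used.
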